## **Appendix C    Systemic corticosteroids routes**

### **Route**

Buccal

Enteral

Administration Via Hemodialysis

Intraarterial

Intraduodenal

Intraesophageal

Intragastric

Intraileal

Intrajejunal

Intraluminal

Intralymphatic

Intramuscular

Intramuscular or Subcutaneous

Intravascular

Intravenous

Intravenous Bolus

Intravenous Drip

Intraventricular

Nasogastric

Oral

Oral Gavage

Oromucosal

Oropharyngeal

Parenteral

Percutaneous

Rectal

Subcutaneous

Sublingual

Submucosal

Transdermal

Mucosal

## Appendix D EQ-5D-5L Scoring

```
* Creation of variable :qsstresn ;
data qs1;
  set adsd.QS_all;
  where QSSTAT ne 'NOT DONE';
  if index(qsorres,"NO")>0 or index (qsorres,"NOT")>0
  then qsstresn=1;
  else if index(qsorres,"SOME") or index(qsorres,"MODERATE") or index(qsorres,"MODERATELY")
  then qsstresn=2;
  else if index(qsorres,"CONFINED") or index(qsorres,"UNABLE") or index(qsorres, "EXTREME") or
index(qsorres, "EXTREMELY")
  then qsstresn=3;
  else qsstresn=.;

run;

proc sort data=qs1 out=qs2;
  by usubjid visit QSTESTCD;
run;

data qs3;
  set qs2;
  by usubjid visit QSTESTCD;
  retain qsstreni profil;
  *****Mobility*****;
  if QSTESTCD="QS1" and qsstresn=1 then qsstreni=1;
  if QSTESTCD="QS1" and qsstresn=2 then qsstreni=1-0.069;
  if QSTESTCD="QS1" and qsstresn=3 then qsstreni=1-0.314;
  if QSTESTCD="QS1" then if qsstresn=. then profil=0; else profil=qsstresn;
  *****Self-care*****;
  if QSTESTCD="QS2" and qsstresn=1 then qsstreni=qsstreni;
  if QSTESTCD="QS2" and qsstresn=2 then qsstreni=qsstreni-0.104;
```

```
    if QSTESTCD="QS2" and qsstresn=3 then qsstreni=qsstreni-0.214;
    if QSTESTCD="QS2" then if qsstresn=. then profil=compress(profil!!0); else
profil=compress(profil!!qsstresn);
    *****Usual activities*****;
    if QSTESTCD="QS3" and qsstresn=1 then qsstreni=qsstreni;
    if QSTESTCD="QS3" and qsstresn=2 then qsstreni=qsstreni-0.036;
    if QSTESTCD="QS3" and qsstresn=3 then qsstreni=qsstreni-0.094;
    if QSTESTCD="QS3" then if qsstresn=. then profil=compress(profil!!0); else
profil=compress(profil!!qsstresn);
    *****Pain/discomfort*****;
    if QSTESTCD="QS4" and qsstresn=1 then qsstreni=qsstreni;
    if QSTESTCD="QS4" and qsstresn=2 then qsstreni=qsstreni-0.123;
    if QSTESTCD="QS4" and qsstresn=3 then qsstreni=qsstreni-0.386;
    if QSTESTCD="QS4" then if qsstresn=. then profil=compress(profil!!0); else
profil=compress(profil!!qsstresn);
    *****Anxiety/depression*****;
    if QSTESTCD="QS5" and qsstresn=1 then qsstreni=qsstreni;
    if QSTESTCD="QS5" and qsstresn=2 then qsstreni=qsstreni-0.071;
    if QSTESTCD="QS5" and qsstresn=3 then qsstreni=qsstreni-0.236;
    if QSTESTCD="QS5" then if qsstresn=. then profil=compress(profil!!0); else
profil=compress(profil!!qsstresn);
    output;
    if last.visit then do;
        qsstresn=profil;

        if index(profil,'3') ne 0 then qsstreni=qsstreni-0.269;
        if index(profil,'2') ne 0 or index(profil,'3') ne 0 then qsstreni=qsstreni-0.081;
            else if profil=0 then qsstreni=.;
                else qsstreni=qsstreni;
        QSTESTCD='QS6';
        QSTEST='Total score';
        QSORRES='';
        QSSTRESC='';
        output;
    end;
run;
```

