#### *2.1.3.2.10 Change from baseline in total score of EuroQol Questionnaire, 5 level system (EQ-5D-5L) endpoint*

EQ-5D is a generic measure of health status developed by the EuroQol Group in order to provide a simple, measure of health for clinical and economic appraisal. It was designed for self-completion by patients.

EQ-5D-5L is planned to be measured at Visit 2 (Day 1) predose, Visit 8 (Week 36), Visit 9/EOT (Week 52) and Visit 10/EOS (Week 64).

EQ-5D-5L is the 5-level system for the 5-dimensional format of the EQ-5D and covers the measurement of mobility, self-care, usual activities, pain/discomfort and anxiety/depression. Each dimension has 5 levels: no problems, slight problems, moderate problems, severe problems, and extreme problems. Scores on the 5 levels are used to create an index score derived from population weights. The United Kingdom population-based scoring will be used to derive an index score from -0.594 to 1.0 renamed the EQ-5D-5L total score.

In addition, the EQ-5D has a single visual analogue scale (VAS) (0-100) to evaluate perceived current health.

Of note: There should be only one response for each dimension. Missing values can be coded as '9' and ambiguous values (e.g. 2 boxes are ticked for a single dimension) should be treated as missing values (2).

Further explanations are available in [Appendix D](#).

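### SAP Appendix D scores the five-level EQ-5D with a three-level program, so slight and severe answers carry no weight and a patient with severe problems can score 1.0

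*SAP*

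**What the plan says.** SAP section 2.1.3.2.10 describes the instrument: "Each dimension has 5 levels: no problems, slight problems, moderate problems, severe problems, and extreme problems". It then says "The United Kingdom population-based scoring will be used to derive an index score from -0.594 to 1.0 renamed the EQ-5D-5L total score", and points to Appendix D for further explanation.

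Appendix D is a SAS program that sorts the answer text into three codes:

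- Code 1: "if index(qsorres,'NO')>0 or index (qsorres,'NOT')>0"
- Code 2: "else if index(qsorres,'SOME') or index(qsorres,'MODERATE') or index(qsorres,'MODERATELY"
- Code 3: "else if index(qsorres,'CONFINED') or index(qsorres,'UNABLE') or index(qsorres, 'EXTREME') or" a variant of the last word
- Any other text: the branch beginning "else qsstresn" sets the answer to missing.

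The program holds weights for codes 1, 2 and 3 only. The running score is carried from record to record by "retain qsstreni profil". It is set afresh only in the mobility step, by "if QSTESTCD='QS1' and qsstresn=1 then qsstreni=1" and the two matching lines for codes 2 and 3. The total is set to missing only when all five answers are unclassified.

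The resulting total is summarised at baseline (section 2.1.1). It is also the outcome and the baseline covariate of an MMRM tested at a two-sided 10% level, qw first and then q2w (sections 2.4.4.2.3.6 and 2.4.4.3).

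**The concern.** Two of the five answers a patient can give have no place in the scoring program. Unclassified answers are neither rejected nor flagged. They pass through as if the patient had no problem in that dimension or, for mobility, they leave the previous record's total in place as the starting value.

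An index built this way can rise when a patient gets worse, and some of its values depend on how the data set happens to be sorted. Quality of life is a listed secondary objective, and the index is formally tested. If Appendix D is run as printed, the estimates, confidence intervals and tests for this endpoint will be computed on values that do not measure health status.

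**Working it through.** **Inputs.** The five labels and the index range come from SAP section 2.1.3.2.10; the weights come from Appendix D.

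| Dimension | Code 2 | Code 3 |
|---|---|---|
| Mobility | 0.069 | 0.314 |
| Self-care | 0.104 | 0.214 |
| Usual activities | 0.036 | 0.094 |
| Pain/discomfort | 0.123 | 0.386 |
| Anxiety/depression | 0.071 | 0.236 |

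Extra terms: 0.081 if any dimension has code 2 or 3, and a further 0.269 if any has code 3. Score = 1 − sum of weights − extra terms.

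**Assumption.** The stored answers use the section 2.1.3.2.10 labels in upper case. The `index` function is case-sensitive, and the questionnaire text is not reproduced in the documents at hand.

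**Step 1: reproduce the plan's own range.** All dimensions at code 3: 1 − (0.314 + 0.214 + 0.094 + 0.386 + 0.236) − 0.269 − 0.081 = 1 − 1.244 − 0.350 = −0.594. All at code 1 gives 1.0. The stated range is therefore exactly that of the three-level weights.

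**Step 2: classify the five labels.** No → 1, slight → missing, moderate → 2, severe → missing, extreme → 3.

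**Step 3: score single patterns.** Levels are written 1 (no) to 5 (extreme), in the order of the table.

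| Pattern | Meaning | Calculation | Score |
|---|---|---|---|
| 11121 | slight pain only | 1 − 0 | 1.000 |
| 11131 | moderate pain only | 1 − 0.123 − 0.081 | 0.796 |
| 11141 | severe pain only | 1 − 0 | 1.000 |
| 11151 | extreme pain only | 1 − 0.386 − 0.269 − 0.081 | 0.264 |
| 13333 | four moderate | 1 − (0.104 + 0.036 + 0.123 + 0.071) − 0.081 | 0.585 |
| 14444 | four severe | 1 − 0 | 1.000 |
| 44444 | all severe | all unclassified | missing |

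The index is not monotone: going from moderate to severe pain alone adds 1.000 − 0.796 = 0.204. The same direction of error appears in every one of the 4 × 3 × 5³ = 1,500 moderate-to-severe changes in a single dimension from self-care to anxiety, with mobility at no, moderate or extreme.

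**Step 4: mobility slight or severe.** No line in the mobility step applies, so the score starts from the retained value. Pattern 41111 returns −0.594, 0.796 or 1.000 when the preceding total was −0.594, 0.796 or 1.000. Records are sorted by patient, visit and item, so the preceding total can belong to the same patient's other visit or to another patient, possibly in another arm.

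**Step 5: extent over the possible patterns.**

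- Total patterns: 5⁵ = 3,125.
- No slight or severe answer: 3⁵ = 243. At least one: 3,125 − 243 = 2,882 (92%).
- Mobility slight or severe: 2 × 5⁴ = 1,250. Of these, 2⁵ = 32 have all five answers unclassified and are set to missing, leaving 1,250 − 32 = 1,218 that start from a carried-over value.
- Mobility at no problems and score 1.000: 3⁴ = 81, of which 81 − 2⁴ = 65 contain at least one severe answer.

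**Step 6: likely size of one error.** The documents give no five-level weights, so a corrected score cannot be computed. If severe pain is assumed to lie between the code's own moderate and extreme values, its score would fall between 0.264 and 0.796. The coded 1.000 is then too high by 0.204 to 0.736.

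**The case against.** The strongest argument is about scope. The EQ-5D-5L change is exploratory and is tested at 10%, outside the 5% sequence for the primary and disease progression endpoints. Quality of life is also measured by the SGRQ and by the EQ-5D visual analogue scale, neither of which uses this index. That is correct, and it means the main conclusions are not at risk.

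It can also be said that the same program is applied to all arms, so under no effect on responses the mis-scoring does not by itself favour one arm. That is fair, and no directional bias or inflation of type I error has been shown. It does not make the comparison useful, because a difference in an index that rises with deterioration cannot be read as benefit or harm.

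Three limits on the figures stand:

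- The statement that worsening from moderate to severe is scored as improvement applies to self-care, usual activities, pain and anxiety with mobility classified. For mobility the fault is carry-over. For example, 31111 scores 1 − 0.069 − 0.081 = 0.850, and 41111 at the next record also scores 0.850. Pattern 33333 scores 0.516, and 43333 after it scores 0.516 − 0.334 − 0.081 = 0.101.
- The 92% weights all patterns equally. The documents give no response frequencies, so the share of affected patients is unknown.
- The scores depend on how the text is stored. With another case, or with digits, the classification would fail more widely. No storage format, however, lets three codes with three sets of weights represent five levels.

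Finally, section 2.1.3.2.10 treats ambiguous answers as missing but gives no rule for the index when a dimension is missing. Setting the index to missing is a choice, though one in line with section 2.4.4.2.3.6, which plans no imputation of a missing week 52 total.

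**Conclusion.** The concern holds. Appendix D contradicts section 2.1.3.2.10. It gives slight and severe answers no decrement in four dimensions, and in mobility it lets the total carry over from a preceding record. A patient with mobility unaffected and four severe dimensions scores 1.000, while the same four at moderate score 0.585. Any pattern with a slight or severe answer (2,882 of 3,125) is mis-scored or set to missing. The individual scores rest on the assumption of upper-case answers in the SAP's wording; the mismatch between three codes and five levels does not. The effect is confined to one exploratory endpoint, but that endpoint is pre-specified and tested, and its values would be wrong if the plan were followed as written.

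**What to change.** Replace Appendix D with a program that:

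1. maps each of the five answers in every dimension to a value set made for the five-level instrument, or to a documented mapping from five levels to an existing value set, and names that source in section 2.1.3.2.10;
2. resets the running score and the profile at the start of every visit of every patient;
3. sets the index to missing if any dimension is missing or ambiguous, with that rule stated in the text;
4. reports any answer text that matches no level as a data query.

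Restate the index range to match the chosen value set; −0.594 to 1.0 is the range of the current three-level weights. Before use, check that all 3,125 patterns are scored, and that the score never rises when one dimension worsens.

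The cost is one SAP appendix and a short program, with no new data. Visits with a missing dimension will drop out of the index.

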## Appendix E MedDRA codelists for AESIs and related hepatic disorder

[figure not shown]
[figure not shown]
requested list	type (cmq, smq, others)	name or code (cmqname, smqcd, others)			description (cmqdesc or SMQ_ShortName, others)	scope (smq) / prim_sec (soc)
reqlist	type	Codename			desc	scope
Acute renal failure	CMQ	GLB_ACUTE RENAL FAILURE NARROW			Acute renal failure Narrow	Narrow
Tuberculosis	CMQ	GZ402673_TUBERCULOSIS			Tuberculosis	
Anaphylactic reactions or acute allergic reactions that require immediate treatment	CMQ	GLB_ANAPHYLACTIC REACTION NARROW			Anaphylactic reaction Narrow	Narrow
Hepatic disorder	CMQ	GLB_HEPATIC DISORDERS NARROW	Hepatic disorders Narrow	Narrow	Hepatic disorders Narrow	Narrow

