10.4.1.3 Adverse event of special interest

An adverse event of special interest (AESI) is an AE (serious or non-serious) of scientific and medical concern specific to the Sponsor's product or program, for which ongoing monitoring and immediate notification by the Investigator to the Sponsor is required. Such events may require further pre-specified investigation/monitoring in order to characterize and understand them. Adverse events of special interest may be added or removed during a study by protocol amendment.

- Pregnancy of a female subject entered in a study as well as pregnancy occurring in a female partner of a male subject entered in a study with IMP

Pregnancy occurring in a female patient entered in the clinical trial or in a female partner of a male patient entered in the clinical trial. It will be qualified as an SAE only if it fulfills one of the seriousness criteria (see [Section 10.4.1.2](#)).

- In the event of pregnancy in a female participant, IMP should be discontinued.
- Follow-up of the pregnancy in a female participant or in a female partner of a male participant is mandatory until the outcome has been determined.

- Symptomatic overdose (serious or non-serious) with IMP
 - An overdose (accidental or intentional) with the IMP is an event suspected by the Investigator or spontaneously notified by the patient and defined as at least twice the intended dose during an interval of less than 5 days.
Of note, asymptomatic overdose has to be reported as a standard AE.
- Increase in ALT $\geq 3 \times \text{ULN}$ (if baseline ALT $< \text{ULN}$) or $\geq 2 \times$ baseline value (if baseline ALT $\geq \text{ULN}$). See the “Increase in ALT” flowchart in [APPENDIX F](#) of the protocol).
- Other project specific AESI (s):
 - 
 - Anaphylactic reactions or acute allergic reactions that require immediate treatment (refer to [APPENDIX D](#) for definition of Anaphylaxis)
 - Severe injection site reactions (see [APPENDIX E](#))
 - Tuberculosis or initiation of medications for suspected tuberculosis
 - Acute renal failure (see [APPENDIX F](#)).

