10.4.6 Guidelines for management of specific laboratory abnormalities

Decision trees for the management of certain laboratory abnormalities by Sanofi are provided in [APPENDIX F](#).

The following laboratory abnormalities should be monitored, documented, and managed according to the related flow chart in protocol appendices.

- Neutropenia
- Thrombocytopenia
- Increase in ALT
- Acute renal insufficiency
- Suspicion of rhabdomyolysis

NOTE: However, if a seriousness criterion is met, the Sponsor is informed immediately (ie, within 1 working day) using the corresponding screens in the eCRF, following the same process as described for the SAEs.

Table 2 - Summary of adverse event reporting instructions

Event category	Reporting timeframe	Specific events in this category	Case Report Form completion		
			AE form	Safety Complementary Form	Other specific forms
Adverse Event (non-SAE, non-AESI)	Routine	Any AE that is not SAE or AESI	Yes	No	No
Serious Adverse Event (non-AESI or AESI)	Expedited (within 24 hours)	Any AE meeting seriousness criterion per Section 10.4.1.2	Yes	Yes	No
Adverse Event of Special Interest	Expedited (within 24 hours)	Pregnancy	Yes	Yes	No
		Symptomatic overdose	Yes	Yes	No
		ALT \geq 3 ULN (if baseline ALT<ULN) and ALT \geq 2 x baseline (if baseline ALT \geq ULN)	Yes	Yes	Yes
			Yes	Yes	Yes
		Anaphylactic reactions or acute allergic reactions	Yes	Yes	Yes
		Severe injection site reactions	Yes	Yes	Yes
		TB or initiation of medications for suspected TB	Yes	Yes	Yes
Acute renal failure	Yes	Yes	No		

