10.6.3 Systemic allergy reaction

10.6.3.1 Anaphylaxis

Allergic reaction is a potential risk associated with the administration of most therapeutic monoclonal antibodies.

Acute allergic reactions may be defined as allergic reaction-mediated signs and symptoms experienced by patients during or shortly after the pharmacologic or biologic agent is given. These reactions may present in a variety of ways, including dizziness, headache, anxiety, dyspnea, hypotension, tachycardia, pruritus, rash, urticarial/angioedema, flushing, nausea, or vomiting. Anaphylaxis may represent the most severe form of infusion reaction, but these events may also occur via other immune-mediated mechanisms (e.g. cytokine-mediated). Allergic reactions may begin within few hours and persist up to 24 hours post dosing. Refer to [APPENDIX D](#) “Definition of anaphylaxis”, which describes the clinical criteria for the diagnosis of anaphylaxis.

Patients should be monitored by site personnel or visiting nurse (if injection performed at patient’s home) for at least 30 minutes after each administration of investigational product for any signs or symptoms of a hypersensitivity reaction.

[For Czech Republic only, per local requirement: Patients should be monitored at the study site by site personnel for at least 2 hours after the first administration of IMP and at least 1 hour after the next 5 administrations for any signs or symptoms of a hypersensitivity reaction. For the subsequent IMP administrations, patients should be monitored by site personnel or visiting nurse (if injection performed at patient’s home) for at least 30 minutes after each administration of IMP.]

Patients should be treated symptomatically if any AEs are observed. General Allergic Reaction and/or Local Injection Site Reaction Complementary Form will have to be completed.

Sometimes transient injection site reactions, irritant in nature, may occur, requiring no intervention and being of dubious significance. These reactions would not be considered to be allergic reactions, and should only be recorded on the Local Injection Site Reaction Complementary Form.

The IMP should be immediately interrupted (temporarily discontinued) if there is a suspicion of an allergic event related to IMP. Refer to [Section 10.4.1.3](#) for hypersensitivity reactions to be reported as AESIs, and to [Section 10.3](#) for hypersensitivity reactions requiring permanent treatment discontinuation.

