All treatment-emergent SAEs will be presented by primary SOC, HLGT, HLT, and PT, showing number (%) of patients with at least 1 serious TEAE, sorted by SOC internationally agreed order. The other levels (HLGT, HLT, PT) will be presented in alphabetical order. Listings will be provided for all SAEs by treatment group and patient with flags indicating on-treatment status.

Analysis of all TEAEs leading to permanent treatment discontinuation

TEAEs leading to treatment discontinuation will be presented by primary SOC, HLGT, HLT, and PT, showing number (%) of patients with at least 1 TEAE leading to permanent treatment discontinuation, sorted by SOC internationally agreed order. The other levels (HLGT, HLT, PT) will be presented in alphabetical order. Listings will be provided for all TEAE leading to permanent treatment discontinuation by treatment group and patient.

Analysis of treatment-emergent AESI

Treatment-emergent AESI, by AESI category and PT, will show number (%) of patients overall, sorted by decreasing incidence of PT within each AESI category. The AESIs include, but are not limited to, the following categories and details of the MedDRA coding will be provided in the statistical analysis plan: tuberculosis, anaphylaxis, hypersensitivity, vasculitis.

Analysis of Deaths

The following deaths summaries will be generated:

- Number (%) of patients who died by study period (TEAE, on-study) and reasons for death summarized on the safety population by treatment received
- Death in nonrandomized patients or randomized and not treated patients
- TEAE leading to death (death as an outcome on the AE e-CRF page as reported by the Investigator) by primary SOC, HLG, HLT and PT showing number (%) of patients sorted by internationally agreed order of SOC and alphabetic order of HLG, HLT, and PT.

Analysis of the laboratory data

The summary statistics (including number, mean, median, standard deviation, minimum and maximum) of all laboratory variables will be calculated for each visit or study assessment (baseline, each post-baseline time point, endpoint) by treatment group. Listings will be provided with flags indicating the out of range values as well as the PCSA values.

The incidence of PCSA at any time will be summarized by treatment group for each laboratory parameter. Shift tables showing changes with respect to the baseline status will be provided.

Analysis of the vital signs data

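### The SAP shows a selector for only one limb of the allergic-reaction AESI, so treated non-anaphylactic acute allergic reactions would probably be missing from the AESI outputs

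*SAP*

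**What the plan says.** Protocol Section 10.4.1.3 lists this AESI as "Anaphylactic reactions or acute allergic reactions that require immediate treatment". Table 2 in Protocol Section 10.4.6 keeps both limbs in its row "Anaphylactic reactions or acute allergic reactions", with reporting within 24 hours and a specific form in addition to the AE form. Protocol Section 11.4.3 names AESI categories for analysis as "tuberculosis, anaphylaxis, hypersensitivity, vasculitis", so anaphylaxis and hypersensitivity are separate entries. It leaves the MedDRA coding to the SAP.

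SAP Section 2.1.4.1 repeats the two-limb label under a Hypersensitivity heading, says that one customized query list selects it, and refers to Appendix E. The Appendix E row carries the same two-limb label and gives a single list, "GLB_ANAPHYLACTIC REACTION NARROW", described as an anaphylactic reaction list with narrow scope. The only other item under the Hypersensitivity heading is severe injection site reactions, selected by high level term and intensity. In SAP Section 2.4.5.1 the AESI table and listing use these selections, and the additional tabulation for this area counts patients with an anaphylaxis event.

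**The concern.** The row label promises two kinds of event, and the selector is named for one of them. SAP Section 2.1.4.1 refers to the protocol for the full AESI descriptions, and the table of changes in SAP Section 1.5 mentions no narrowing. A reader of the report would therefore take the row to cover both limbs. If few events appeared in it, the reader would conclude that acute allergic reactions needing treatment were rare in each arm, although such events may only have been coded elsewhere.

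This category matters here. Protocol Section 10.6.3.1 names allergic reaction as a potential risk of most therapeutic monoclonal antibodies. The protocol also puts effort into documenting these events, with expedited reporting, a dedicated form and, for allergic events involving the skin, dermatology review with unscheduled PK and ADA samples (Section 10.6.3.2). The planned exploration of ADA against safety in SAP Section 2.4.7 could also lose information if it draws on this AESI category.

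**Working it through.** No arithmetic applies, and the plan gives no figure to reproduce. The check follows the AESI from its definition to its outputs.

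1. **Are the two limbs different events?** Protocol Section 10.6.3.1 describes acute allergic reactions broadly: "These reactions may present in a variety of ways, including dizziness, headache, anxiety, dyspnea, hypotension, tachycardia, pruritus, rash, urticarial/angioedema" and further symptoms. It then says that "Anaphylaxis may represent the most severe form of infusion reaction". Protocol Appendix D gives three alternative criteria for anaphylaxis. Take isolated acute urticaria that needs immediate treatment:
   - Criterion 1 needs skin or mucosal involvement plus respiratory compromise or reduced blood pressure (or end-organ symptoms). Only the skin element is present, so it is not met.
   - Criterion 2 needs at least two of four elements (skin-mucosal, respiratory, blood pressure, gastrointestinal). One of four is present, so it is not met.
   - Criterion 3 needs reduced blood pressure. It is not met.

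   The event is thus an AESI under the second limb without being anaphylaxis under any criterion. The second limb has content of its own.

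2. **Does the SAP select both limbs?** For this AESI, Section 2.1.4.1 shows one route, a code list, and Appendix E shows one list, named and scoped for anaphylactic reaction. The visible text gives no allergic-reaction or hypersensitivity query, no tick box and no use of a complementary form for it. Nothing applies the condition that immediate treatment was needed.

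3. **Does another AESI rule pick up the remainder?** Only in part. The severe injection site reaction rule captures severe local reactions. It does not capture systemic reactions or local reactions below severe intensity.

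4. **Which outputs inherit the selection?** In SAP Section 2.4.5.1 these are the AESI table by category and preferred term, the AESI listing, and the separate count of patients with an anaphylaxis event.

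5. **Where would unselected events still appear?** In the same section: the TEAE tables by arm (by system organ class and preferred term, by relationship, by maximal severity), the serious TEAE tables and listings, and the tables of TEAEs leading to treatment discontinuation.

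One AESI bullet in Section 2.1.4.1 and one tabulation line in Section 2.4.5.1 are redacted, and some figures in Appendix E are not shown. None of these is counted as a gap. The row for this AESI is visible and complete.

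**The case against.** The strongest objection is that the content of the list is unknown. A reader might infer that non-anaphylactic reactions certainly fall outside the AESI tables. The documents do not support that. They show the list's name, description and scope but not its terms, and Appendix E assigns it to the full two-limb label. If it holds some broader allergic terms, the loss is partial. This stands, and it limits the conclusion to a probable omission.

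A reader might also infer that these events would be absent from the comparison between arms. That is not supported either. They stay in the by-arm TEAE tables. Protocol Section 10.4.1.2 counts severe hypersensitivity reactions needing intensive emergency or home treatment as medically important, so those reach the SAE tables. Protocol Section 10.3.3 lists symptoms of severe hypersensitivity among the reasons for permanent discontinuation, so those reach the discontinuation tables. What is at risk is grouping under the prespecified category, mainly for treated, non-serious systemic reactions.

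It is also tempting to argue from the tick boxes used for pregnancy and symptomatic overdose. That argument is weak: tuberculosis and acute renal failure are also selected by code list, and ALT increase by laboratory data. The visible text shows no investigator AESI flag for allergic reactions, so none should be presumed.

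Finally, the sentence on the most severe form speaks of infusion reactions, whereas this product is given subcutaneously, and the AESI bullet refers only to the anaphylaxis criteria in Appendix D. Both points are fair. They do not remove the second limb, which Section 10.4.1.3 and Table 2 state outright, or the separate hypersensitivity category in Section 11.4.3.

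**Conclusion.** The selection rule shown in the SAP covers one limb of a two-limb AESI. Judged by the list's name and narrow scope, treated acute allergic reactions short of anaphylaxis would probably be missing from the AESI table and listing, and from the anaphylaxis count. The conclusion assumes that the list's terms match its name.

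The number of patients affected cannot be derived: neither the list's terms nor any expected rate of such reactions is in the documents. The loss could range from none, if the list is broader than its name, to every treated acute allergic reaction not coded to an anaphylaxis term and not caught by the severe injection site rule. The consequence is confined to safety display. Under SAP Section 2.4.5 the safety analysis is essentially descriptive with no systematic testing, and no efficacy analysis is affected. The change is still worth making, because the row label would otherwise claim more than its selector is shown to deliver.

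**What to change.** In SAP Section 2.1.4.1 and Appendix E, define the category as the union of two parts and report each part separately by arm:

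- events selected by the anaphylaxis list;
- other adverse events with a General Allergic Reaction complementary form and corrective treatment recorded.

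The sources are already planned. Table 2 of the protocol requires a specific form for this AESI. When adverse events are observed after dosing, Protocol Section 10.6.3.1 says that the "General Allergic Reaction and/or Local Injection Site Reaction Complementary Form will have to be completed". Corrective treatment is recorded for each adverse event under Protocol Section 10.4.3, and the AESI listing in SAP Section 2.4.5.1 already shows it. The rule should rest on the General Allergic Reaction form rather than the local reaction form, because Section 10.6.3.1 sends transient irritant site reactions to the local form only. An investigator AESI flag should be used only if the e-CRF has one.

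The downside is that corrective treatment is a proxy for a need for immediate treatment, so some milder or delayed reactions may be included. Showing the two parts separately keeps the anaphylaxis count clean and makes this visible.

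If the rule is not added, relabel the row as anaphylaxis only and record in SAP Section 1.5 the departure from Protocol Sections 10.4.1.3 and 11.4.3. Either way the cost is SAP wording and at most one additional selection rule, with no new data collection.
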